12.2.2. Primary Endpoint: Slope of eGFR

For the final analysis of the primary endpoint (eGFR slope) evaluated following the initial acute effect of randomized treatment (ie, eGFR chronic slope over 2 years) in non-US countries and following the initiation of randomized treatment (ie, eGFR total slope over 2 years) in the US, the ability of the study to distinguish between treatment groups was evaluated using the projected treatment difference in eGFR slopes given the treatment difference on the surrogate efficacy endpoint. The calculations assume that treatment difference in eGFR slope is equal to the treatment difference in UP/C response proportions multiplied by the difference in eGFR slopes among patients who achieved the UP/C response (ie, UP/C responders) and those who do not (ie, UP/C non-responders). Available data from the DUET and disease registry studies were used to model this relationship.

Using the available data, the modeling exercise yielded an estimated difference in eGFR slopes between UP/C responders and non-responders of approximately 8.4 mL/min/1.73 m² per year based on the eGFR chronic slope. With the assumed treatment difference in response proportions of 30%, the projected treatment difference in eGFR slopes is approximately 2.52 mL/min/1.73 m² per year. The model also estimated the residual variability (SD) to be approximately 10.80 mL/min/1.73 m² per year. Power calculations follow the approach described in Dupont and Plummer (Dupont 1998).

Based on the eGFR total slope, the modeling exercise yielded a projected treatment difference in eGFR slopes of approximately 2.1 mL/min/1.73 m² per year, assuming a treatment difference in response proportions of 30% for the surrogate endpoint. With 300 patients (approximately 150 patients per treatment group) and a 2-sided α of 0.05, the study has at least 90% power to differentiate between treatments. This power calculation is based on the Wald statistic using a standard deviation of the eGFR total slope of 5.50 mL/min/1.73 m² per year estimated from blinded interim data from the current study.

It should be noted that statistical testing can only be performed at the final analysis if a statistically significant difference is demonstrated at the interim analysis of the surrogate endpoint.

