For the primary endpoint of slope of eGFR evaluated following initiation of randomized treatment (ie, from Day 1 to Week 108; total slope over 2 years), a mixed-effects model will be fitted to the available eGFR data. The response variable is the eGFR measured at post-baseline assessments for each patient during the double-blind period. The model will include fixed effects for treatment, both stratification factors for randomization, baseline eGFR (continuous), time (in weeks) from baseline (continuous), and time-by-treatment interaction. The model will also include a random intercept and a random slope for each patient. The mixed model will utilize restricted maximum likelihood estimation with Kenward-Roger method used to compute the denominator degrees of freedom for tests of fixed effects. The model will assume an unstructured covariance matrix. If the model does not converge under the unstructured covariance matrix, the autoregressive-1 covariance structure will be used.

The primary efficacy hypothesis of interest is whether eGFR slopes over the blinded treatment period (after adjusting for early hemodynamic effects) are different between the 2 treatment groups, ie:

$$H_0: \beta_{\text{time}*\text{treatment}} = 0 \text{ versus}$$

$$H_1: \beta_{\text{time}*\text{treatment}} \neq 0.$$

This hypothesis will be tested using the mixed model by testing whether the time-by-treatment interaction parameter LS mean estimate is equal to zero.

Sensitivity analyses are planned to assess the potential impact of major protocol deviations, premature treatment discontinuations, changes in immunosuppressive medications, and the choice of the change point.

12.7.1.2. Surrogate Efficacy Endpoint: Proportion of Patients Achieving a UP/C ≤ 1.5 g/g (170 mg/mmol) and a $>40\%$ Reduction from Baseline at Week 36

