4.3. Sample Size Considerations

4.3.1. Sample Size Justifications

Approximately 300 patients will be randomized and allocated 1:1 to receive sparsentan or irbesartan. This sample size takes into consideration enrollment feasibility in this rare disease setting and was evaluated using simulations.

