7.7. Blinded Assessment of Comparability to Previous Study Populations

A statistical modeling exercise was conducted to support the design of this Phase 3 study. The modeling was performed using data from NEPTUNE, FSGS-CT, and DUET. The patient population included in the modeling was selected from these data sources to reflect the target patient population in DUPLEX. The modeling results ([Statistical Analysis Plan Modeling Report \[FSGS\], v1.0](#)) indicate that there is a relationship between eGFR slope and FPRE status across data sources. The exercise resulted in a model that reasonably predicts treatment difference in eGFR slopes given a treatment difference in FPRE response proportion, adjusting for potential prognostic factors. This relationship is key in establishing the utility of FPRE as a likely surrogate for early assessment of efficacy.

The applicability of the modeling results to the DUPLEX study lies in the comparability of the patient populations used in the modeling with that of the DUPLEX population. While it is reasonable to expect comparability due to the manner in which patients were selected for inclusion in the modeling, an assessment of population comparability is planned when approximately 190 patients have been randomized and while the study is still completely blinded. These 190 randomized patients constitute the same patient population used in the sensitivity analysis of the surrogate endpoint at the time of interim analysis described in [Section 6.6.2.2](#).

The comparability assessment will focus on baseline and demographic characteristics explored as potential prognostic factors in the previous modeling exercise. Continuous variables (ie, age, log UP/C, and eGFR) will be compared using t-tests. Categorical variables (ie, sex, race, and eGFR \leq or >120 mL/min/1.73m²) will be compared using chi-square tests. The specified baseline and demographic characteristics from DUPLEX will be compared against the corresponding variables from each of the following analysis datasets: NEPTUNE, FSGS-CT, DUET, pooled NEPTUNE + FSGS-CT, pooled DUET + NEPTUNE, and pooled NEPTUNE + FSGS-CT + DUET. Comparability of the DUPLEX population with a specific analysis dataset will be concluded if the null hypotheses of no difference for any of the 6 variables are not rejected at 2-sided $\alpha = 0.05$ following the Benjamini-Hochberg procedure to control the family-wise error rate.

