8.5. Analysis of the Primary Efficacy Endpoint

8.5.1. Primary Efficacy Analysis

8.5.1.1. eGFR Chronic Slope over 2 Years

The primary efficacy analysis will be based on the FAS. The eGFR chronic slope over 2 years, defined as the slope of eGFR following the initial acute effect of randomized treatment (ie, Week 6 to Week 108), will be analyzed via a mixed-effects model with linear spline (ie, a 2-slope model with knot or change point at Week 6) with available eGFR data at the final analysis. The response variable is the eGFR measured at on-treatment, post-baseline assessments during the randomized treatment period for each patient. The model will include the following fixed effects:

- Treatment group (2 levels: sparsentan, irbesartan)
- Baseline eGFR
- Time from baseline (analysis visit, in weeks)
- Time from change point (in weeks)
- Treatment group by time from baseline interaction
- Treatment group by time from change point interaction
- Randomization stratification variable (4 levels based on Screening eGFR and UP/C)

In addition, the model will also include a random intercept and random slopes (time from baseline and time from change point) for each patient. The mixed model will utilize restricted maximum likelihood estimation with Kenward-Roger method to compute the denominator

degrees of freedom for tests of fixed effects. An unstructured covariance matrix will be assumed. If convergence issues arise, the autoregressive-1 covariance structure will be used.

The associated slope estimates within treatment group, difference in slopes, 95% CI, and 2-sided p-value will be extracted from the model. The treatment effect for the slope following the change point at Week 6 (ie, difference in slopes) will be the sum of the coefficients for the treatment group by time from baseline interaction and treatment group by time from change point interaction estimated from the model. Slope and the difference in slopes will be annualized for ease of presentation and interpretation.

8.5.1.2. eGFR Total Slope over 2 Years

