The primary efficacy analysis will be based on the FAS. The eGFR total slope over 2 years, defined as the slope of eGFR following the initiation of randomized treatment (ie, Day 1 to Week 108), will be analyzed via a mixed-effects model with available eGFR data at the final analysis. The response variable is the eGFR measured at on-treatment, post-baseline assessments during the randomized treatment period for each patient. The model will include the following fixed effects:

- Treatment group (2 levels: sparsentan, irbesartan)
- Baseline eGFR
- Time from baseline (analysis visit, in weeks)
- Treatment group by time from baseline interaction
- Randomization stratification variable (4 levels based on Screening eGFR and UP/C)

In addition, the model will also include a random intercept and random slope for each patient. The mixed model will utilize restricted maximum likelihood estimation with Kenward-Roger method to compute the denominator degrees of freedom for tests of fixed effects. An unstructured covariance matrix will be assumed. If convergence issues arise, the autoregressive-1 covariance structure will be used.

The associated slope estimates within treatment group, difference in slopes, 95% CI, and 2-sided p-value will be extracted from the model. The treatment effect will be the contrast between sparsentan and irbesartan marginal slope estimates. Slope and the difference in slopes will be annualized for ease of presentation and interpretation.

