8.7. Analysis of the Secondary Efficacy Endpoints

8.7.1. Percent Change of eGFR from Week 6 to Week 108

The percent change of eGFR from Week 6 to Week 108 will be analyzed at the final analysis based on the FAS, using MMRM. The dependent variable will be all available on-treatment natural log(eGFR) data from Week 2 to Week 108. The model will include the following fixed effects:

- Treatment group (2 levels: sparsentan, irbesartan)
- Baseline eGFR in log scale
- Visit (categorical)
- Treatment group by visit interaction
- Randomization stratification variable (4 levels based on Screening eGFR and total urine protein)

In addition, patient will be included as a random effect.

The model will utilize restricted maximum likelihood estimation with Kenward-Roger method used to compute the denominator degrees of freedom for tests of fixed effects. An unstructured covariance matrix will be assumed. If convergence issues arise, autoregressive-1 covariance structure will be used.

Statistical significance of the treatment effect at Week 108 will be assessed by comparing with the treatment effect at Week 6. The LS mean estimate from the MMRM model will be used to perform treatment group comparisons. Estimates and CIs will be converted to percentages via the following transformations:

$$[\exp(\text{least squares mean change from Week 6 in natural log(eGFR)}) - 1] \times 100$$

Robustness of the analysis due to missing data and premature treatment discontinuations will be explored by the following sensitivity analyses:

- MMRM using multiple imputation
- MMRM using treatment completers only (patients who completed blinded treatment)

To assess the impact of changes in immunosuppressive medications, the analysis will be repeated by excluding assessments after initiation or intensification of immunosuppressive medication in the blinded treatment period.

To assess the potential impact of patient evaluability and major protocol deviations, the analysis will be repeated using the PP Analysis Set.

8.7.2. Change in eGFR from Baseline to 4 Weeks Post-cessation of Randomized Treatment (Week 112)

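### The eGFR slope models adjust the level of eGFR, but not its slope, for the randomisation strata; if the strata predict slope, the tests are conservative and some precision goes unused

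*SAP*

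**What the plan says.** The two primary models in SAP 8.5.1 are built alike. The fixed effects are treatment, baseline eGFR, time and "Randomization stratification variable (4 levels based on Screening eGFR and UP/C"; the chronic-slope model adds time from the Week 6 change point. Only treatment interacts with time: "Treatment group by time from baseline interaction", plus the matching term for time from the change point in the spline model. Each patient has a random intercept and random slope(s). Protocol 12.7.1.1 has the same structure; after treatment, its total-slope model lists "both stratification factors for randomization, baseline eGFR (continuous), time (in weeks) from baseline (continuous), and time-by-treatment interaction". No sensitivity analysis in SAP 8.5.2 lets a stratum or baseline variable interact with time.

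For percent change from Week 6 to Week 108, SAP 8.7.1 uses an MMRM in which, again, only treatment interacts with visit. The test is a difference of two visit effects: "Statistical significance of the treatment effect at Week 108 will be assessed by comparing with the treatment effect at Week 6".

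Randomisation is by permuted blocks, stratified by screening eGFR and UP/C (SAP 4.4). For the total slope, Protocol 12.2.2 takes an SD of 5.50 from blinded interim data and a projected difference of 2.1 mL/min/1.73 m² per year. At 150 per arm, tested two-sided at 5%, it concludes: "the study has at least 90% power to differentiate between treatments. This power calculation is based on the Wald statistic".

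**The concern.** A main effect moves a patient's whole eGFR line up or down; it does not tilt it. The tested quantity is a difference in tilt. If eGFR falls faster in some strata than in others, these models have nowhere to put that except the random-slope variance, and that variance sets the standard error.

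Blocked randomisation within strata keeps the arms nearly balanced on stratum, so stratum differences in slope largely cancel from the treatment comparison. The estimate is then more stable than its reported standard error says. The interval is too wide, the test rejects less than 5% of the time under the null, and some power is forgone. In SAP 8.7.1 a covariate effect that is constant over visits cancels from the Week 108 minus Week 6 contrast (exactly so with complete data), so the same reasoning applies there. At stake is efficiency in a trial whose size was set partly by enrolment feasibility in a rare disease (SAP 4.3.1).

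**Working it through.** **Inputs from the documents (total slope).** "Approximately 300 patients will be randomized and allocated 1:1 to receive sparsentan or irbesartan" (SAP 4.3.1), so 150 per arm; SD 5.50; difference 2.1; two-sided α 0.05 (Protocol 12.2.2, SAP 4.3.1.2).

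**Step 1: reproduce the plan's figure.** SE = 5.50 × √(2/150) = 0.635. Power = Φ(2.1/0.635 − 1.96) = 91.1%, which agrees with the stated figure. Nothing says that stratum differences in slope were removed from the 5.50, so it takes no stated credit for the strata.

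**Step 2: what the missing term does.** Let R² be the share of slope variance (5.50²) that comes from stratum differences in mean slope. The documents do not give it, so it is varied here as an assumption.

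- Reported SE, main effects only: 0.635 whatever R² is.
- True sampling SD with balanced strata: 0.635 × √(1 − R²).
- Ratio of reported to true: 1/√(1 − R²).
- Actual type I error: 2 × [1 − Φ(1.96/√(1 − R²))].
- Power, main effects only: Φ((2.1 − 1.96 × 0.635)/true SD).
- Power with stratum-by-time: Φ(2.1/true SD − 1.96).

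| Assumed R² | True SD | SE too wide by | Actual type I error | Power, main effects only | Power with stratum-by-time | Total N for 90% power with the term |
|---|---|---|---|---|---|---|
| 0 | 0.635 | 0% | 5.0% | 91.1% | 91.1% | 290 |
| 5% | 0.619 | 2.6% | 4.4% | 91.7% | 92.4% | 274 |
| 10% | 0.603 | 5.4% | 3.9% | 92.2% | 93.6% | 260 |
| 20% | 0.568 | 11.8% | 2.8% | 93.4% | 95.9% | 232 |

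**Step 3: what R² might look like.** Suppose 45% of patients are in the high-UP/C stratum (an assumption). A slope gap of g between the two UP/C strata gives R² = 0.45 × 0.55 × g²/5.50²: 3.3% for g = 2, 7.4% for g = 3 and 20.5% for g = 5 mL/min/1.73 m² per year. The gaps are also assumptions.

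**Step 4: simulation check.** 3,000 trials per setting, with 300 patients, four strata, permuted blocks, random intercept and slope, and complete data; the baseline eGFR and strata distributions were assumed.

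- R² = 0: reported SE 0.636 against empirical SD 0.635; the two models agree.
- R² = 10%: main effects only, 0.637 against 0.610, power 91.2%. With stratum-by-time, 0.602 against 0.609, power 93.2%.
- R² = 20%: main effects only, 0.637 against 0.568, type I error 2.6%, power 93.6%. With stratum-by-time, 0.568 against 0.567, type I error 5.0%, power 96.2%.

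An intercept–slope correlation of −0.3 gave similar results.

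**What these figures do not cover.** They are for the total slope only. The chronic-slope calculation rests on a residual SD of 10.80 and a regression power method (SAP 4.3.1.2), with no between-patient slope variance given, so the percentages cannot be carried over. No figure was computed for SAP 8.7.1. Dropout was not modelled, although the slope models use on-treatment values only and follow-up will be unequal.

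**The case against.** The strongest reply is that nothing the plan promises fails. The stated power reproduces without credit for the strata, type I error is not inflated, no bias is shown, and the direction is conservative. The loss exists only if the strata predict slope, and no slope difference between strata is reported. All of this stands; it makes the point an available efficiency gain rather than a defect in validity.

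Some stronger readings are tempting, but the documents do not support them.

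- *That the stratified randomisation is ignored.* The four-level stratum variable is a fixed effect in both slope models and in SAP 8.7.1, and SAP 8.1 weights LS means by observed strata proportions. Only its interaction with time or visit is missing.
- *That the planned slope gap of 8.4 shows how strongly the strata predict slope.* That figure compares UP/C responders with non-responders (SAP 4.3.1.2), a post-baseline outcome. Protocol Section 4 says that patients with nephrotic-range proteinuria do poorly without treatment, which makes some relation plausible but gives no size.
- *That leaving out baseline log UP/C is an error.* SAP 7.7 names it among "baseline and demographic characteristics explored as potential prognostic factors in the previous modeling exercise", but for comparing study populations; it does not report which factors predicted slope. UP/C already enters through the strata.
- *That the standard error is also overstated because of baseline eGFR.* The overstatement comes from balance on the strata. For baseline eGFR or log UP/C beyond the strata, omitting a time interaction costs some precision but does not bias the standard error.

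**Conclusion.** The point holds as a conditional statement about efficiency. The strata and baseline eGFR adjust eGFR level in SAP 8.5.1.1, 8.5.1.2 and 8.7.1 and in Protocol 12.7.1.1, but not the slope or the Week 6 to Week 108 change being tested. If the strata predict slope, the tests are conservative and somewhat less powerful than the design allows; if not, nothing is lost.

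The gain at the planned difference is small partly because power is already high. At a true difference of 1.5 (an assumption), the Step 2 formulas give Φ((1.5 − 1.245)/0.603) = 66% against Φ(1.5/0.603 − 1.96) = 70% for R² = 10%, where 1.245 = 1.96 × 0.635. For R² = 20% they give 67% against 75%.

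The size rests on an R² that the documents do not supply, on complete data and on the total-slope inputs. For the chronic slope and SAP 8.7.1 the direction carries over, but the size is unknown.

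**What to change.** Before unblinding for the final analysis, amend the SAP, and align the protocol wording, as follows:

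- **8.5.1.2 (total slope):** add stratum-by-time.
- **8.5.1.1 (chronic slope):** add stratum-by-time and stratum-by-time-from-change-point.
- **8.7.1:** add stratum-by-visit.
- **Within-arm slopes:** state that they are averaged over the observed strata proportions, extending to slopes the weighting that SAP 8.1 sets for LS means.

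The tested treatment contrasts do not change. Baseline-eGFR-by-time (by visit in 8.7.1) is an optional further gain in precision. Log baseline UP/C with its time interaction is likewise an optional addition.

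The cost is SAP and protocol wording, with no new data. Four strata give 3 extra parameters in the total-slope model and 6 in the spline model. In 8.7.1 the 13 scheduled visits from Week 2 to Week 108 give 3 × 12 = 36, which is more but still modest for repeated measures on about 300 patients.

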3.2. Study Endpoints

3.2.1. Primary and Surrogate Efficacy Endpoints

The primary efficacy endpoint is the slope of estimated glomerular filtration rate (eGFR) over approximately 2 years of randomized treatment assessed at the final analysis. The slope of eGFR is evaluated following the initial acute effect of randomized treatment (ie, from Week 6 to Week 108; chronic slope over 2 years) in non-United States (US) countries and following initiation of randomized treatment (ie, from Day 1 to Week 108; total slope over 2 years) in the US.

The surrogate efficacy endpoint is the proportion of patients achieving the FSGS partial remission endpoint (FPRE), defined as urine protein/creatinine ratio (UP/C) ≤ 1.5 g/g (170 mg/mmol) and a $>40\%$ reduction from baseline of the double-blind period in UP/C at Week 36 at the interim analysis.

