4.3.1.2. Primary Endpoint: Slope of eGFR

For the final analysis of the primary endpoint (eGFR slope) evaluated following the initial acute effect of randomized treatment (ie, eGFR chronic slope over 2 years) in non-US countries and following the initiation of randomized treatment (ie, eGFR total slope over 2 years) in the US, the ability of the study to distinguish between treatment groups was evaluated using the projected treatment difference in eGFR slopes given the treatment difference on the surrogate efficacy endpoint. The calculations assume that treatment difference in eGFR slope is equal to the treatment difference in UP/C response proportions multiplied by the difference in eGFR slopes among patients who achieved the UP/C response (ie, UP/C responders) and those who did not (ie, UP/C non-responders). Available data from the DUET and disease registry studies were used to model this relationship.

Using the available data, the modeling exercise yielded an estimated difference in eGFR slopes between UP/C responders and non-responders of approximately 8.4 mL/min/1.73 m² per year based on the eGFR chronic slope. With the assumed treatment difference in response proportions of 30%, the projected treatment difference in eGFR slopes is approximately 2.52 mL/min/1.73 m² per year. The model also estimated the residual variability (standard deviation [SD]) to be approximately 10.80 mL/min/1.73 m² per year. With 300 patients (approximately 150 per treatment group) and a 2-sided α level of 0.05, the study has at least 90% power to differentiate between treatments if the underlying eGFR slope difference is at least 2.5 mL/min/1.73 m² per year. With 300 patients, the minimum treatment difference in eGFR slope that can be declared statistically significant is approximately 1.40 mL/min/1.73 m²/year. Power calculations follow the approach described in Dupont and Plummer (Dupont 1998).

Based on the eGFR total slope, the modeling exercise yielded a projected treatment difference in eGFR slopes of approximately 2.1 mL/min/1.73 m² per year, assuming a treatment difference in

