4.3.2. Sample Size Reassessment

A sample size reassessment (SSR) procedure is planned when the first 50 randomized patients have completed the Week 60 visit or discontinued study medication/study prior to Week 60. This procedure will be conducted and overseen by the Data Monitoring Committee. An analysis plan specific to the SSR will be approved prior to the SSR.

Using the methodology described by Mehta and Pocock ([Mehta 2011](#)), the conditional power for the endpoint of slope of eGFR over the treatment period will be computed. If the conditional power is in the range of 50% to 80%, the sample size will be increased to raise power, subject to a maximal increase in N of 35% (ie, total N will not exceed 300*1.35). In line with Gao, Mehta, and Ware ([Gao 2008](#)), there is no Type I error inflation with this approach. If the conditional power is not in the range 50% to 80%, the trial will proceed with no change in sample size. The same SSR methodology will be applied separately to both eGFR chronic and total slope endpoints, and the sample size will be increased according to the larger of the 2 results, subject to the same maximal increase of up to 35%. Note that in the SSR analysis plan, the eGFR total slope endpoint was labeled as starting from Week 2 to Week 108. While a more accurate label is from Day 1 to Week 108, the data and model used to estimate the eGFR total slope is the same as those described in this SAP.

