8. EFFICACY

8.1. General Considerations

All efficacy analyses will be based on the FAS or IAS, as described below. The primary, surrogate, and secondary endpoint analyses will also be performed on the PP Analysis Set as supportive analyses. All primary efficacy analyses based on laboratory data will use central lab data only. All efficacy analyses specified below refer to the double-blind period only.

UP/C will be determined using first morning void urine samples and will be calculated as the geometric mean of 3 first morning void urine samples collected within 5 days prior to the visit. If one of the samples is missing, the average of the other 2 samples will be used. As UP/C is a highly right-skewed variable, analyses will be performed on log-transformed data. For ease of interpretation, results will be presented in the original units.

The eGFR for each baseline and post-baseline visit will be determined using the CKD-EPI (Levey 2009) formula for patients ≥ 16 years of age at the time of screening and the Modified Schwartz formula for patients < 16 years of age at the time of screening (Schwartz 2009a; Schwartz 2009b).

For the purposes of efficacy analyses, an assessment is considered “on treatment” if it occurs after the first dose of study medication and no more than 3 days after the date of last dose of randomized treatment.

For all least-squares (LS) means that include strata coefficients, the observed strata proportions will be used instead of assuming equal sizes of strata.

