8.5.2. Sensitivity Analyses of the Primary Efficacy Endpoint

Robustness of the primary analysis of the primary efficacy endpoint due to missing data or premature treatment discontinuations (including the impact of COVID-19) will be explored by the following sensitivity analyses:

- Mixed-effects model (as described in [Section 8.5.1.1](#) and Section 8.5.1.2) with multiple imputation
- Tipping point approach of the multiple imputation analysis, as described in [Section 6.6.1.2.2](#)

- Mixed-effects model (as described in [Section 8.5.1.1](#) and [Section 8.5.1.2](#)) using treatment completers only (patients who completed blinded treatment)
- Mixed-effects model (as described in [Section 8.5.1.1](#) and [Section 8.5.1.2](#)) including local lab data

To assess the robustness of choice of change point, the primary efficacy analysis of eGFR chronic slope over 2 years will be repeated using a different change point at Week 4 and Week 8.

To assess the impact of changes in immunosuppressive medications, the primary efficacy analysis will be repeated by excluding assessments after initiation or intensification of immunosuppressive medication in the blinded treatment period.

To assess the potential impact of patient evaluability and major protocol deviations, the primary efficacy analysis will be repeated using the PP Analysis Set.

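### The US primary is labelled a Day 1 to Week 108 eGFR slope, but the tested coefficient rests on post-first-dose data with a free treatment intercept, and no Day 1-anchored slope analysis is planned

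*SAP*

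**What the plan says.** SAP 8.5.1.2 describes the US primary, the total slope, as "defined as the slope of eGFR following the initiation of randomized treatment (ie, Day 1 to Week 108"; Protocol 12.7.1.1 uses the same interval. For the model's outcome, SAP 8.5.1.2 says: "The response variable is the eGFR measured at on-treatment, post-baseline assessments during the randomized treatment period for each patient". SAP 8.1 counts an assessment as on treatment only "if it occurs after the first dose of study medication and no more than 3 days after the date of last dose of randomized treatment", and the first eGFR analysis visit in SAP 6.5.4 (Table 2) is Week 2. Fixed effects are treatment, baseline eGFR, time, treatment-by-time and randomization stratum. The reported treatment effect is the difference in slopes.

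SAP 4.3.2 says that "in the SSR analysis plan, the eGFR total slope endpoint was labeled as starting from Week 2 to Week 108". It continues: "While a more accurate label is from Day 1 to Week 108, the data and model used to estimate the eGFR total slope" are unchanged from those in the SAP.

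For the non-US primary, SAP 3.2.1 says: "The slope of eGFR is evaluated following the initial acute effect of randomized treatment". Whether the acute phase is included is therefore what separates the two regional primaries.

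In SAP 8.5.2, the total-slope sensitivity analyses are multiple imputation, tipping point, treatment completers, local laboratories, exclusion of data after immunosuppressive changes, and the Per Protocol set. All reuse the same model. The change-point check covers the other endpoint only: "eGFR chronic slope over 2 years will be repeated using a different change point at Week 4 and Week 8".

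The total-slope hypothesis in the protocol (Synopsis and 12.7.1.1) carries a parenthesis saying early hemodynamic effects are adjusted for. SAP 8.2 omits it for the US primary.

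**The concern.** A slope that starts on Day 1 should reflect whatever happens to eGFR between Day 1 and the first visits. In this model nothing ties the fitted lines to the Day 1 level. Each arm has its own intercept, so an early separation that then persists is absorbed as a level shift, and that shift is not tested. Moving the label from Week 2 to Day 1 does not bring a Day 1 value into the response.

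At stake is how a significant US result is described. It would be reported as a net Day 1 to Week 108 benefit, although the tested coefficient may leave out much of an early loss or gain. The protocol's leftover parenthesis adds to the ambiguity, because it suggests the acute effect is meant to be removed.

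**Working it through.** **Inputs.** Visits at Weeks 2, 4, 6, 8, 12, then every 12 weeks to 108, which is 13 visits (SAP 4.1). Change point at Week 6 (SAP 8.5.1.1). Total-slope difference 2.1 and SD 5.50 mL/min/1.73 m² per year, 150 per arm, 2-sided alpha 0.05 (SAP 4.3.1.2). The acute difference is set to 1 mL/min/1.73 m² as a unit; the documents give no value.

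**1. The plan's own figure.** SE = 5.50 × √(2/150) = 0.635. Then 2.1/0.635 − 1.96 = 1.35, giving power 91.1%. The stated power of at least 90% reproduces.

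**2. Benchmark.** The documents say only that the endpoint is a slope. I take the Day 1-anchored slope as the Week 108 difference divided by elapsed time: 108/52.18 = 2.07 years. An acute difference of 1 that persists moves it by 1/2.07 = 0.483 per year.

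**3. What the planned model returns.** With complete visits and a random intercept and slope, generalized least squares equals ordinary least squares for the treatment intercept and slope, so no variance assumption is needed.

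- Mean visit time = 560/13 = 43.08 weeks.
- Sxx = 41,160 − 560²/13 = 17,036.9.
- Slope per week = Σ(t − 43.08)(y − 1)/Sxx, where y is the acute difference at visit t. Only visits before the build is complete contribute.

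Linear build to Week 6: y = 1/3 at Week 2, 2/3 at Week 4, then 1.

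- Sum = 41.08 × 2/3 + 39.08 × 1/3 = 40.41.
- Slope = 40.41/17,036.9 = 0.00237 per week = 0.124 per year.
- Share = 0.124/0.483 = 26%.
- Intercept = 0.923 − 0.00237 × 43.08 = 0.82.

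Linear build to Week 12: sum = 41.08 × 10/12 + 39.08 × 8/12 + 37.08 × 6/12 + 35.08 × 4/12 = 90.51, so slope = 0.00531 per week = 0.277 per year.

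| Acute difference complete by | Tested slope per year | Share of 0.483 | Taken by untested intercept | Missed per year |
|---|---|---|---|---|
| Week 2 | 0 | 0% | 100% | 0.483 |
| Week 4 (linear) | 0.063 | 13% | 91% | 0.420 |
| Week 6 (linear) | 0.124 | 26% | 82% | 0.359 |
| Week 12 (linear) | 0.277 | 57% | 59% | 0.206 |

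For scale, 0.359 per 1 mL/min of acute difference is 17% of the planning difference of 2.1 (0.359/2.1) and 57% of the SE (0.359/0.635). The sign follows the sign of the acute difference.

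**4. Dropout.** Under assumed covariances and exponential on-treatment dropout, the Week 6 share rises to 28–30% at 20% dropout and 32–37% at 40%.

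**5. Which remedy works.** Adding Day 1 to the response while keeping a free treatment intercept still leaves 69–84% of the acute difference in the intercept. A common Day 1 mean with a single straight line depends heavily on the assumed variance components. A common Day 1 mean with a Week 6 spline and the contrast (6 × acute + 102 × chronic)/108 recovers about 65%, 86%, 100% and 117% of builds complete by Weeks 2, 4, 6 and 12.

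**The case against.** The strongest reply is that the benchmark is already available. SAP 8.8.1.3 plans an MMRM of absolute eGFR change from baseline at every visit. Its Week 108 difference divided by 2.07 years is the quantity used above, with no knot or linearity assumption. SAP 8.7.2 adds change from baseline to Week 112, with a robustness analysis at 4 weeks after end of treatment. This stands: a reader who infers that nothing anchored to baseline is planned would be wrong. But the MMRM is exploratory and not linked to the primary. The Week 112 test is off randomized treatment, limited to those who completed 108 weeks, and third in the US hierarchy.

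It is also fair that the model is openly specified, that the benchmark is mine, and that both arms take the initial half dose until Week 2 (SAP 4.2.1), so the 0% case requires the whole effect to appear before titration. The proposed spline also depends on the shape of the acute effect.

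Four stronger readings are tempting, and the documents do not support them:

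- *The planned test favours sparsentan.* No acute between-arm eGFR difference is stated. Protocol 8.3.1 reports greater blood-pressure lowering than irbesartan in hypertension studies, but in DUET blood pressure changed little with sparsentan exposure. An acute gain on sparsentan would make the planned slope too small.
- *The gap between the projected chronic slope (2.52) and total slope reveals an acute loss.* SAP 4.3.1.2 says only that "the modeling exercise yielded a projected treatment difference in eGFR slopes of approximately 2.1", from the assumed response difference. It attributes nothing to an acute effect.
- *Type I error is inflated.* The null in SAP 8.2 is equal slopes. Rejecting when fitted slopes differ but net Week 108 change does not is not a false rejection of that null.
- *The model always misses most of an acute effect.* For a build to Week 12, 57% reaches the slope.

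**Conclusion.** The mismatch between label and tested coefficient is real and should be corrected. For an acute between-arm difference complete by the SAP's own Week 6 knot, the tested slope carries 0–26% of its contribution to a Day 1-anchored slope; for a build to Week 12 it carries 57%. These shares assume complete visits, an acute difference that persists, and a benchmark of Week 108 difference over 2.07 years. They need no variance assumption. The actual bias is unknown in size and direction, and is zero if there is no acute difference and the treatment effect is linear. What is missing is an anchored slope analysis and a statement of how the primary should be read.

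**What to change.** 1. Add to SAP 8.5.2 a total-slope sensitivity analysis with Day 1 eGFR in the response, a Day 1 mean common to both arms, no treatment main effect, baseline eGFR dropped as a covariate, strata kept, a Week 6 spline, and the contrast (6 × acute + 102 × chronic)/108. Repeat it with knots at Week 4, (4 × acute + 104 × chronic)/108, and Week 8, (8 × acute + 100 × chronic)/108. Report beside it the planned MMRM Week 108 difference divided by 2.07 years, which needs no knot.
2. State in SAP 8.5.1.2 that the tested slope is estimated from Week 2 to Week 108 data and largely excludes a between-arm difference arising by about Week 6. A significant result should be read with the anchored results before it is described as a net Day 1 to Week 108 benefit.
3. Delete the parenthesis on early hemodynamic effects from the protocol's total-slope hypothesis (Synopsis and 12.7.1.1), to match SAP 8.2.

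The cost is one extra model and some wording. It needs no new data and leaves the primary test, alpha and sample size reassessment unchanged. The spline's shape dependence (about 65% recovery of a difference complete by Week 2, about 117% of a build to Week 12) is why the knot-free MMRM figure belongs beside it.
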